Will you obtain a Certificate of Confidentiality for this study?

No

Please further discuss any potential confidentiality issues related to this study.

Section L: Cost/Payment

Delineate clinical procedures from research procedures. Will subject's insurance (or subject) be responsible for research related costs? If so state for which items subject's insurance (or subject) will be responsible (surgery, device, drugs, etc). If appropriate, discuss the availability of financial counseling.

Patients will not be charged to participate and all ensuant costs to the research will be covered by the study grant.

If subjects will be paid (money, gift certificates, coupons, etc.) to participate in this research project, please note the total dollar amount (or dollar value amount) and distribution plan (one payment, pro-rated payment, paid upon completion, etc) of the payment.

Dollar Amount:

100

Distribution Plan:

Single payment following receipt of final specimen. In instances of fetal or neonatal or infant demise, remuneration will occur with last specimen received.

The rationale for deferring payment until the final specimen is received, rather than by study visit, is that the design of the study requires complete data sets.

Section M: Genetics

How would you classify your genetic study?

Discuss the potential for psychological, social, and/or physical harm subsequent to participation in this research. Please discuss, considering the following areas: risks to privacy, confidentiality, insurability, employability, immigration status, paternity status, educational opportunities, or social stigma.

Not applicable, as this a microbiome metagenomics study and host DNA is not analyzed.

Will subjects be offered any type of genetic education or counseling, and if so, who will provide the education or counseling and under what conditions will it be provided? If there is the possibility that a family's pedigree will be presented or published, please describe how you will protect family member's confidentiality?

Not applicable.

Section N: Sample Collection

SAMPLE: Other: Vagina

What is the purpose of the sample collection?

With respect to the vagina and upper genital tract, it is well established that among reproductive aged women the composition of the vaginal microbiota is affected by several host factors including age, menarche, sexual activity, and exogenous exposures such as the use of certain contraceptives and “feminine hygiene” products. It is presumed that these alterations confer protection against the overgrowth of potentially pathogenic microbes. For example, at menarche lactobacilli are the dominant organisms but even among healthy women anaerobic bacteria and *Candida* species are easily detected with traditional culture methodology. Similarly, bacterial vaginosis (BV) is a common “disease” in as great as 20% of women and manifests following polymicrobial overgrowth dominated by *Gardnerella* and anaerobic bacteria such as *Prevotella*. Of interest to our proposal herein, the precise pathogenic organisms contributing to the clinical syndrome of BV remains unknown although recent advances with high throughput molecular approaches (i.e., terminal RFLP) suggests that additional phylotypes may be primary contributors.

This study involves broad determination of the microbiota found in vagina during pregnancy. This study will enroll gravidae at 28 weeks gestation. The participation of healthy individuals will create a baseline for discovery of the core microbiota in association with adverse pregnancy conditions. All subjects will be between the ages of 18 and 40. The age range of subjects has been established based on reproductive capacity and in consideration of our other studies which have provided reference data.

Specifically, swabs will be obtained from the vaginal introitus, the mid vagina, and the posterior fornix.

For blood draws, specify the amount drawn, in teaspoons, at each visit and across the course of the subjects entire participation time.

Not applicable.

Is there the possibility that cell lines will be developed with this sample?No

Sample will be obtained from:

Other: Clinic

Will the sample be stripped of identifiers?

Yes

If sample will be released outside the hospital:

Will sample be released to anyone not listed as an investigator on the protocol? Will the information be identifiable, coded or de-identified?

No

Will sample material be sold or transferred to any third parties? Will the information be de-identified?

No

If sample will be banked for future use:

Where will the sample be banked and for how long?

The sample will be in the locked laboratory and locked -80 freezer of [name] or designated co-Investigator at Baylor College of Medicine indefinitely.

Does the banking institution have an approved policy for the distribution of samples?

Not applicable.

If the entire sample will NOT be used during the course of this research study:

Will the remaining tissue be discarded? If not what will be done with the remaining sample after study completion and how long will the sample be kept?

The sample will be in the locked laboratory and locked -80 freezer of [name] or designated co-Investigator at Baylor College of Medicine indefinitely.

Will samples be made available to the research subject (or his/her medical doctor) for other testing?

No

If a subject withdraws from the study:

Will subject have the option to get the remaining portion of their sample back?

No

Will samples be destroyed? If not, will they be kept anonymously? What will happen to the sample if the subject revokes authorization?

Destroyed if revoked.

Will data obtained from their sample be deleted? What will happen to the sample if the subject revokes authorization?

Yes.

Will study data or test results be recorded in the subject's medical records?

No

Will results of specific tests and/or results of the overall study be revealed to the research subject and or his/her doctor?

No.

Please identify all third parties, including the subject's physician, to receive the test results.

None.

SAMPLE: Genetic Material

What is the purpose of the sample collection?

Placental swabs will be collected for microbiome profiling.

For blood draws, specify the amount drawn, in teaspoons, at each visit and across the course of the subjects entire participation time.

NA

Is there the possibility that cell lines will be developed with this sample? No

Sample will be obtained from:

Other: Labor and delivery

Will the sample be stripped of identifiers?

No

If sample will be released outside the hospital:

Will sample be released to anyone not listed as an investigator on the protocol? Will the information be identifiable, coded or de-identified?

No.

Will sample material be sold or transferred to any third parties? Will the information be de-identified?

No.

If sample will be banked for future use:

Where will the sample be banked and for how long?

The sample will be in the locked laboratory and locked -80 freezer of [name] or designated co-Investigator at Baylor College of Medicine indefinitely.

Does the banking institution have an approved policy for the distribution of samples?

Not applicable.

If the entire sample will NOT be used during the course of this research study:

Will the remaining tissue be discarded? If not what will be done with the remaining sample after study completion and how long will the sample be kept?

The sample will be in the locked laboratory and locked -80 freezer of [name] or designated co-Investigator at Baylor College of Medicine indefinitely.

Will samples be made available to the research subject (or his/her medical doctor) for other testing?

No

If a subject withdraws from the study:

Will subject have the option to get the remaining portion of their sample back?

No

Will samples be destroyed? If not, will they be kept anonymously? What will happen to the sample if the subject revokes authorization?

Destroyed on revoke.

Will data obtained from their sample be deleted? What will happen to the sample if the subject revokes authorization?

Destroyed on revoke.

Will study data or test results be recorded in the subject's medical records?

No

Will results of specific tests and/or results of the overall study be revealed to the research subject and or his/her doctor?

No.

Please identify all third parties, including the subject's physician, to receive the test results.

None.

SAMPLE: Tissue

What is the purpose of the sample collection?

Stool (first meconium and at 1 and 6 months of age) will be collected for determination of the fetal and infant microbiome.

For blood draws, specify the amount drawn, in teaspoons, at each visit and across the course of the subjects entire participation time.

Not applicable.

Is there the possibility that cell lines will be developed with this sample?No

Sample will be obtained from:

Other: nursery, parent

Will the sample be stripped of identifiers?

Yes

If sample will be released outside the hospital:

Will sample be released to anyone not listed as an investigator on the protocol? Will the information be identifiable, coded or de-identified?

If released to our collaborative investigators within the NCS, all information will be coded.

Will sample material be sold or transferred to any third parties? Will the information be de-identified?

No.

If sample will be banked for future use:

Where will the sample be banked and for how long?

The sample will be in the locked laboratory and locked -80 freezer of [name] or designated co-Investigator at Baylor College of Medicine indefinitely.

Does the banking institution have an approved policy for the distribution of samples?

If samples are requested by other NCS investigators, an approved IRB from their institution as well as a materials transfer agreement between the institutions will first be arranged.

If the entire sample will NOT be used during the course of this research study:

Will the remaining tissue be discarded? If not what will be done with the remaining sample after study completion and how long will the sample be kept?

Yes. The sample will be in the locked laboratory and locked -80 freezer of [name] or designated co-Investigator at Baylor College of Medicine indefinitely.

Will samples be made available to the research subject (or his/her medical doctor) for other testing?

No

If a subject withdraws from the study:

Will subject have the option to get the remaining portion of their sample back?

No

Will samples be destroyed? If not, will they be kept anonymously? What will happen to the sample if the subject revokes authorization?

Destroyed on revoke.

Will data obtained from their sample be deleted? What will happen to the sample if the subject revokes authorization?

Yes. Destroyed.

Will study data or test results be recorded in the subject's medical records?

No

Will results of specific tests and/or results of the overall study be revealed to the research subject and or his/her doctor?

No.

Please identify all third parties, including the subject's physician, to receive the test results.

None

Section O: Drug Studies

Is this study placebo-controlled?

No

Does the research involve a drug or biologic (including radioactive drugs) that is not approved by the FDA?

No

Will the research involve a radioactive drug that is not approved by the FDA?

No

IND Number:

Section P: Device Studies

Does this research study involve the use of ANY device?

No

Section Q: Consent Form(s)

Biospecimen Collection and Analysis in the National Children's Study: Microbiome

Biospecimen Collection and Analysis in the National Children's Study: Microbiome (Children's Stool Consent)

Section R: Advertisements

None

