(Primary Objective 1) To establish proven currently utilized methodologies for sample collection and concomitant DNA extraction for metagenomic sequencing from the HMP JumpStart ([name] and [name]) and UH2 Demonstration Projects ([name]) with already scheduled NCS visits and self-sampling. *Sample the vaginal microbiome at the scheduled third trimester NCS clinical visit *Sample the placental and fetal (first meconium) microbiomes at the time of delivery *Self-sample stool microbiomes at scheduled intervals of one month and 6 months

(Primary Objective 2) To develop and refine protocols to enable banking of acquired specimens prior to microbial DNA extraction in an effort to establish feasibility of deferring metagenomic sequencing and analysis of some of the samples collected through NCS, and to enhance ease of collection of high quality specimens in the context of a large multicenter study that can be used for both DNA and RNA extraction and metagenomic/metatranscriptomic analysis.

With our formative approach executed as a one year demonstration project executed jointly by investigators at the Waukesha County Vanguard Center (WCVC) and at Baylor College of Medicine (BCM) employing samples collected in conjuncture with a modified Vanguard protocol, we will demonstrate not only feasibility with easily expanded NCS protocols and HMP metagenomics infrastructure, but the ability to yield unparalleled insight into functional variation of the microbiome across diverse racial and socioeconomic populations with developmental exposures. Of note, it is important to comment that our proposed protocol reflects the ultimate intent by the investigators on this LOI with respect to what will define a “full scale” NCS initiative on microbiome research.

Section E: Protocol Risks/Subjects

E1. Risk Category

(45 CFR 46.404) Category 1: Research not involving greater than minimum risk.

E2. Subjects

Gender:
Both

Age:
Adolescent (13-17 yrs), Adult (18-64 yrs), Infant/Toddler (0-36 mos), Premature Infant (<37 weeks gestational age)

Ethnicity:
All Ethnicities

Primary Language:
English

Groups to be recruited will include:
Both patients and healthy, non-patient, normals

Vulnerable populations to be recruited as subjects:
Children, Emancipated minors, Pregnant women

Vulnerable populations require special protections. How will you obtain informed consent, protect subject confidentiality, and prevent undue coercion?

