Briefly, samples for this formative project collected will include: 1. A vaginal specimen from pregnant women during their third trimester visit (existing time frame with current NCS protocol). 2. At the time of delivery, placental tissue and the infant's first meconium will be collected (existing time frame with current NCS protocol). 3. Subjects will be asked to submit a stool sample from their baby 1 month and 6 months after delivery.

In accordance with the NCS Protocol, subjects will be screened using a modified general health and pregnancy questionnaire and will be examined by an obstetrician-gynecologist at the time of sampling to verify eligibility. Subjects will be pregnant females between the ages of 18 and 40. Subjects who are 16 years old and meet the definition of an emancipated minor in the state of Texas will also be eligible for participation.

Eligible and consented subjects will be enrolled and the vaginal specimen will be collected at the time of the scheduled NCS protocol office visit during the third trimester. Each subject (defined as the gravidae) will provide a total of three sets of specimens: (1) vaginal swab for determination of the vaginal microbiome, taken at a single time point of 28 weeks gestation, (2) placental and fetal (meconium) swab, taken at the time of delivery (or shortly thereafter, dependent upon passage of first meconium sample), for determination of the placental and fetal microbiome. The infant stool samples at the one month and six month reference point will be collected at home using a self-collection kit and then sent to the investigator at Baylor College of Medicine.

Specific subject information will be collected via review of the medical record(s), with information being recorded on health history forms and study specific case report form (so-called NCS minimal data forms, see attachments). After specimen collection and coding, microbial DNA will be isolated from the microbiome specimens. The DNA will then be used to produce DNA sequence information (metagenomics) in accordance with fully functional and existing protocols through the Human Microbiome Project (H-25849, H-22895) and the Burroughs Wellcome Fund Preterm Birth Initiative (H-26589).

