Selection of the study population in this feasibility study for formative research will occur in alliance with current recruitment methodology for the NCS ([name], PI). The target for this multi-center study here at Baylor are 30 gravidae between the ages of 16 and 40. While there are two enrolling sites (Baylor College of Medicine and Waukesha County Vanguard Center (WCVC)), the second enrolling site will operate under their own IRB protocol as mandated by the National Children's Study.

The requisite gestational age range at the time of enrollment will be 28 weeks. A goal for minority participation will be at least 20% of the total number of subjects.

All samples will be sent to and processed by study personnel at Baylor College of Medicine ([name] lab, [name] lab, [name] lab).

For this protocol there is no group assignment, randomization or placebo group.

Inclusion Criteria:

Gravidae 28 weeks of gestation anticipated to undergo delivery at St. Luke's Episcopal Hospital. This will focus our recruitment efforts to subjects under care with Baylor College of Medicine Obstetrics and Gynecology.

Exclusion Criteria:

Gravidae with a non-viable fetus.

F2. Procedure

Vaginal sample collection: Two vaginal swabs in triplicate will be acquired by clinical providers at the time of the scheduled 3rd trimester clinical visit from the vaginal introitus and posterior fornix. As part of eligibility, the gestational age will be determined by the first trimester sonogram and compliance with the third trimester visit. A CatchAll® swab will be employed under direct visualization to sample the vaginal introitus and posterior fornix. The nucleic acid will be stored in SCF-1 buffer media, and transferred to the laboratory for immediate extraction. In the "banking approach", samples will be placed into either (1) RNeasy or (2) SCF-1 media, and thereafter placed on dry ice and stored at -80°C. At approximately 60 days from sample acquisition, nucleic acid extraction will be performed on both banking protocol samples in a small replicate cohort.

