Placental sample collection: At the time of delivery, a CatchAll® swab will be employed under direct visualization to sample in triplicate the placenta on the fetal side in a uniform fashion (4 cm medial to the cord insertion). In the scientific protocol, nucleic acid is again stored in SCF-1 buffer media and transported to the laboratory for immediate extraction. In the "banking approach", samples will be placed into either (1) RNeasy

or (2) SCF-1 media, and thereafter placed on dry ice and stored at -80oC. At approximately 60 days from sample acquisition, nucleic acid extraction will be performed on both banking protocol samples in a replicate cohort (10%).

Meconium and stool sample collection: First meconium samples will be collected in the diaper. For longitudinal stool sample collection, subjects will be instructed to perform self-collection of fecal specimens at home. In addition, a portion of the fecal specimen will be preserved in RNAlater as part of the specimen banking protocol. Briefly, in this demonstration project children and their or guardians will receive at least two sterile plastic collection containers with plastic stool collection frames. They will be instructed to place stool collection frames on the back of the toilet bowl prior to securing the stool container. After defecation, a portion of the specimen will be placed into RNAlater for preservation and banking protocol, and then the stool container will be closed firmly with a plastic lid and placed into a Styrofoam box with cold gel packs. Eight to ten polar gel packs per fecal specimen will be stored for a maximum of 12 hours in a freezer (at subject's home) prior to stool collection. Gel packs will be placed below and around (completely surrounding) stool container within the Styrofoam box. This box will be delivered to the laboratory for immediate nucleic acid extraction. The RNAlater sample will be stored at -80oC. At approximately 60 days from sample acquisition, nucleic acid extraction will be performed on both banking protocol.

DNA extraction: For fresh extraction, samples will arrive in PowerBead tubes provided. For banked approach samples, initial thawing on ice with subsequent sample addition to PowerBead tubes. Nucleic acid is freed with extensive vortexing, and subsequent transfer of supernatant to collection tubes for extraction using filter-based centrifugation in a modified MoBio protocol (HMP MOP, available upon request).

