The majority of sample collection (90 of 120 subjects) will take place at WVCV, where participant enrollment began in 2008 and averages 10 to 12 NCS births per month with anticipated increasing accrual. A smaller cohort of participants (30 of 120 subjects) will be enrolled at BCM.

BCM, although not currently enrolling in the Vanguard pilot, has established and optimized approaches for microbial sampling of vagina, placenta, meconium, and feces, through participation in the HMP JumpStart and HMP Clinical Demonstration Project (UH2) initiatives and will thus serve as a measured control against any methodological concerns related to microbial sampling and nucleic acid extraction (see prior referenced IRB approved protocols).

The combined involvement of these sites will leverage the NCS experience and extensive environmental data collection of WVCV with the HMP metagenomics infrastructure at BCM, and allow us to evaluate the feasibility of adding microbiome sampling and metagenomic analysis to the NCS.

G2. Data Analysis

Provide a description of your plan for data analysis. State the types of comparisons you plan (e.g. comparison of means, comparison of proportions, regressions, analysis of variance). Which is the PRIMARY comparison/analysis? How will the analyses proposed relate to the primary purposes of your study?

Outline of goals and strategies for the collection, analysis, and characterization of metagenomics data from NCS acquired specimens employing established methodology from the HMP JumpStart initiative have been previously outlined.

Briefly, our collaborative proposal will use a two layered analysis strategy.

We will collect microbial specimens (n=120 gravidae, 90 from WVCV and 30 from BCM) at NCS specified timepoints, and aliquot specimens for both fresh extraction and banked specimen protocols. We will extract nucleic acids from at the time of specimen collection and subsequently subject such immediate extractions to flash freezing for later batched-run metagenomic sequencing and analysis. In the second-layer strategy, we will collect parallel samples from each subject for immediate banking (using 1 of 2 "banking" protocols) rather than already proven immediate nucleic acid extraction. A randomly-selected cohort comprising 20% (10% of each of

the two banking protocols) of these “banked” specimens will be run in batched parallel samples in order to establish and refine banking methodology.

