Because this is a feasibility study where the results will not be compared until completion of sequencing of all eligible subject samples, not protocol modifications will be instituted. Once IRB approval is obtained here at BCM, the approved IRB will be sent to the University of Wisconsin for institutional approval. In this feasibility study of minimal risk, no interim analysis is planned.

When research is conducted in collaboration with outside entities or organizations, the PI must obtain the necessary approvals from those entities. The BCM IRB may request documentation that such approvals have been obtained. Please list and describe the planned sites for this multi-site research for which the BCM PI is either Sponsor-Investigator and/or Coordinating Center. Sites that do not meet the requirements for inclusion in section A6a of the protocol summary and BCM informed consent documents should be listed here.

Collaborating Site: Medical College of Wisconsin Waukesha County Vanguard Center (WCVVC)

Section I: Potential Benefits

Describe potential benefits to be gained by the individual subject as a result of participating in the planned work.

Subjects will not derive direct benefit nor treatment for participation.

Describe potential benefits to society of the planned work.

The benefits to society are reflective of the general benefits in acquiring knowledge regarding human health and disease.

In this feasibility study, subjects will not benefit personally from giving the specimens because this research will take a long time to produce medically useful results. However, subjects will be part of a study to help researchers determine feasibility so that they may ultimately gain knowledge and understand more about the human microbiome and how it relates to pregnancy health and disease.

Do anticipated benefits outweigh potential risks? Discuss the risk-to-benefit ratio.

The results of research cannot be foreseen so it is possible that new risks may arise in the future that cannot be predicted now. However, it is believed that the benefits of learning more about the human microbiome and how it relates to health and disease outweigh the current and potential future minimal risks. Therefore, the risk-to-benefit ratio is favorable.

Section J: Consent Procedures

J1. Waiver of Consent

Will this research require a waiver of consent and authorization?

No

Will additional pertinent information be provided to subjects after participation?

No

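### The stated one-year duration cannot hold 120 mother-infant sets with a 6-month stool: at the protocol's own accrual rate the last stool falls at about month 16 to 18

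*Protocol*

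**What the plan says.** - **Duration.** Section D, after the two primary objectives: "With our formative approach executed as a one year demonstration project executed jointly by investigators". It is the only overall duration given. Nothing ties it to enrolment or funding alone.
- **Size.** Section G2: "We will collect microbial specimens (n=120 gravidae, 90 from WVCV and 30 from BCM) at NCS specified timepoints".
- **Accrual.** Section G1 says that the Waukesha site (WCVC, also printed WVCV) "averages 10 to 12 NCS births per month with anticipated increasing accrual". The increase is not quantified.
- **Entry.** Section F1: "The requisite gestational age range at the time of enrollment will be 28 weeks".
- **Last specimen.** Section F1: "Subjects will be asked to submit a stool sample from their baby 1 month and 6 months after delivery". The 6-month stool is also listed under Primary Objective 1, and no section limits it to a subset.
- **Banking.** Section F2, on stool: "At approximately 60 days from sample acquisition, nucleic acid extraction will be performed on both banking protocol". Section G2 runs only part of the banked material: "A randomly-selected cohort comprising 20% (10% of each of" the two banking methods).
- **Comparison.** Section H3 says that "results will not be compared until completion of sequencing of all eligible subject samples". Section G2 has extracted material frozen and sequenced later in batches.

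**The concern.** Follow-up of one woman from entry at 28 weeks to her infant's 6-month stool uses almost nine months of the year, if she delivers at 40 weeks. The larger site needs 7.5 to 9 months to accumulate 90 births. Because the last woman enrolled still has her full follow-up ahead of her, the two periods add.

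This study exists to show feasibility, so a duration that the design cannot meet bears on the question being asked. If the project closed at one year, the 6-month stool would come from early enrollees only, with a site mix different from the one planned. Section L says that the design needs complete data sets and ties payment to the final specimen, so stopping short also conflicts with the design. If the project instead runs until all specimens are in, the stated duration is wrong by several months.

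**Working it through.** **Inputs from the protocol:** 12 months (Section D); 90 + 30 = 120 women and 10 to 12 births per month at WCVC (G1, G2); entry at 28 weeks and stool at 6 months (F1); banked extraction at about 60 days (F2); 20% of banked specimens run (G2); about 900 potential Baylor (BCM) subjects per year (J2).

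**Assumptions, not in the protocol:** delivery at 40 weeks (37 weeks as a variant), every WCVC birth enrolled and retained, and a flat accrual rate. One month is 30.44 days.

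**Step 1. Time per woman.** From 28 to 40 weeks is 12 × 7 / 30.44 = 2.76 months. To the 6-month stool: 2.76 + 6 = 8.76 months. The 60-day step adds 60 / 30.44 = 1.97 months.

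**Step 2. Accrual at WCVC.** 90 / 12 = 7.5 months; 90 / 10 = 9.0 months.

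**Step 3. Calendar for the last WCVC woman.**

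| Milestone | 12 per month | 10 per month |
|---|---|---|
| Entry | 7.5 | 9.0 |
| Delivery (+2.76) | 10.3 | 11.8 |
| 6-month stool (+6) | 16.3 | 17.8 |
| Banked extraction, if that stool is selected (+1.97) | 18.2 | 19.7 |

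The stated 12 months is not reproduced.

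**Step 4. More favourable readings.**
- Delivery at 37 weeks: 9 × 7 / 30.44 = 2.07 months, so the last stool is at 7.5 + 2.07 + 6 = 15.6 to 9.0 + 2.07 + 6 = 17.1 months.
- Clock started at the first birth, banking ignored: 7.5 + 6 = 13.5 to 9.0 + 6 = 15.0 months.

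**Step 5. A less favourable reading.** At 75% uptake (assumed), the last stool is at 7.5 / 0.75 + 8.76 = 18.8 to 9.0 / 0.75 + 8.76 = 20.8 months.

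**Step 6. What 12 months can hold.** The entry window is 12 − 8.76 = 3.24 months. At 10 to 12 per month that gives 32 to 39 WCVC infants with a 6-month stool. BCM has about 900 / 12 = 75 potential subjects per month, or 243 in the window. All 30 could enter in time if about 30 / 243 = 12% took part. The ceiling is therefore 62 to 69 of 120 (52% to 57.5%). BCM would supply 30 / 69 = 43% to 30 / 62 = 48% of it, against a planned 30 / 120 = 25%.

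**Step 7. Rate needed to fit.** 90 / 3.24 = 27.8 per month, which is 2.3 times 12 and 2.8 times 10, from the outset. At 37 weeks the window is 12 − 8.07 = 3.93 months and the rate 22.9 per month (1.9 to 2.3 times). Counted from the first birth it is 90 / 6 = 15 per month (1.25 to 1.5 times). None of these leaves time for sequencing.

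**The case against.** The best defence is that the one-year phrase appears once, as description, and that no sample size, data cut-off or analysis depends on it. It may mean funding or enrolment. The site that sets the pace expects accrual to rise and works under its own IRB protocol, which is not shown. The study is a minimal-risk pilot without randomisation, and a longer calendar biases no estimate. Much of this stands, and it lowers the severity. It does not remove the conflict, because no section restricts the year to funding or enrolment and the expected rise has no figure.

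Two stronger readings are tempting, and the protocol does not support them.

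- *Only a small fraction reaches the end of the schedule within the year.* Deducting the 60 days for every infant leaves a window of 3.24 − 1.97 = 1.27 months, or 13 to 15 WCVC infants. But G2 runs only a random 20% of banked specimens, and the main layer is immediate extraction. The 60-day step therefore does not limit every infant, and 13 to 15 is not the yield of 6-month stool. Fewer infants than 32 to 39 could reach banked extraction by month 12, but only the 20% cohort needs it. A cohort drawn from early enrollees would, however, not be a random sample of all 120.
- *At one year there would be nothing to report.* H3 describes when results are compared, in explaining why no protocol changes are expected, and adds that no interim analysis is planned. It does not forbid a report on the specimens in hand if the project closes early.

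**Conclusion.** The point holds, at moderate severity. The one-year duration, 90 women at 10 to 12 births per month, entry at 28 weeks and stool at 6 months cannot all be true. The overrun is about 4 to 6 months to the last stool (month 16.3 to 17.8), and up to about 8 months if a late stool enters the banked cohort (month 18.2 to 19.7). Batched sequencing comes on top. At the stated rate the last stool falls after month 12 in every variant tried, the shortest being 13.5 months. The main figures rest on delivery at 40 weeks, full uptake and retention, and a flat rate. Earlier delivery shortens them slightly and lower uptake lengthens them. A sharp early rise in accrual could close the gap, but only at the multiples shown in Step 7, and the protocol gives no figure for it.

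**What to change.** Either of two amendments would do:

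1. **Restate the duration** in Section D as about 16 to 18 months to the last stool and up to about 20 months with banked extraction, plus sequencing time. Give the accrual, uptake and delivery assumptions.
2. **Keep a one-year report, but define it.** Limit it to vaginal, placental, meconium and 1-month specimens up to a stated cut-off, with the expected number for each type. Report the 6-month stool in a later dated analysis. On the assumptions above, all 90 WCVC deliveries fall by month 10.3 to 11.8. By month 12, (12 − 2.76 − 1) × 10 = 82 up to the full 90 could have given a 1-month stool. Time for 60-day extraction of the banked cohort and for sequencing would move the cut-off earlier and reduce these numbers. Align the H3 statement on when results are compared with the two reports.

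If one year was meant as an enrolment or funding period, say so and state the full duration beside it.

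The cost is a protocol amendment and a less favourable published timeline, or a smaller stated number for the 6-month stool at one year. No extra subjects or specimens are needed.
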